## III. Second Tier Exploratory Endpoints

Our “second tier endpoints” are exploratory in nature. Our study is not powered for them since existing data in the literature is insufficient to calculate an accurate sample size for these endpoints.

1. We will seek to establish whether a specific psychiatric symptom profile may be associated with the anticipated differential mood improvement in response to escitalopram + celecoxib or escitalopram + PBO. To that end, additional rating instruments have been included (over and above the HAM scales) and detailed assessments will be made of symptom profiles obtained from the rating instruments.
2. We will assess the safety and tolerability of the combination treatment by means of an adverse events symptom checklist and by relevant laboratory measures (e.g., CBC, PT, PTT).
3. Assessment of the efficacy of celecoxib by measuring PGE2 response to assess the extent of COX-2 inhibition.
4. An assessment of blood levels of escitalopram and celecoxib will tell us if these two agents interfere or promote each other's uptake and/or clearance.

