## STUDY TREATMENTS AND COMPLIANCE

Subjects who meet the eligibility criteria will receive one week of single-blinded escitalopram placebo + single-blinded celecoxib placebo. Subjects who continue to meet eligibility at randomization will receive open-label escitalopram (beginning at 10mg/day) + double-blinded treatment of celecoxib (fixed at 400mg/day) or placebo. Escitalopram doses may be optimized based on efficacy and tolerability over the 8 weeks of active treatment. Subjects will be randomized according to a fixed assignment ratio of 1:1 (escitalopram + celecoxib: escitalopram + placebo). Assignment to groups is based on a pharmacy generated randomization code.

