### I. Compliance

To ensure compliance, participants be asked to return all unused medication at the following visit. The returned capsules will be counted. Additionally, blood concentrations of escitalopram and celecoxib will be determined at Baseline, Week 4 and Week 8.

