### Measurement of Blood Levels of Celecoxib and Escitalopram

These measures will be obtained from blood drawn at Baseline, Week 4 and Week 8. Plasma concentrations of celecoxib and escitalopram will be measured using a solid phase HPLC method. This measurement will help the study team determine whether subjects are compliant, adequately dosed and if celecoxib changes escitalopram blood levels, or vice versa. Celecoxib levels will be assayed by collaborating investigators in Munich, Germany. Escitalopram levels will be assayed by collaborating investigators in Charleston, SC.

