## DATA ANALYSIS AND STATISTICAL METHODS

### I. Statistical Analysis

Specific Aim 1 is to determine if combined pharmacotherapy of escitalopram + celecoxib will result in earlier and/or improved affective responses compared to escitalopram + PBO. Additionally, Specific Aim 1 seeks to control for pain perception in this analysis. For this aim, the patients in the two treatment arms will be compared on HAM-D, HAM-A, MADRS, BDI, and BAI scores. This will be accomplished with an analysis of covariance conducted at weeks 1, 2, 4 and 8. Baseline mood scores and McGill Pain Inventory scores will be used as covariates. In addition, the number of patients who are and are not classified as remitters at week 8 (those having a HAM-D score of 7 or less) will be tallied and cross-referenced with treatment group (escitalopram + celecoxib or escitalopram + PBO). The frequencies in the resulting 2-by-2 contingency table will be analyzed with the Pearson Chi-Square Test for Association.

For Specific Aim 2, dealing with treatment safety and tolerability, the numbers of patients who do and do not experience adverse events at weeks 1, 2, 4, and 8 will be tallied and cross-referenced with treatment group. The frequencies in the resulting 2-by-2 contingency table will be analyzed with the Pearson Chi-Square Test for Association. Additionally, to understand whether any pharmacodynamic interaction exists between escitalopram and celecoxib, blood levels of escitalopram and celecoxib drawn at weeks 4 and 8 will be compared for patients in the two treatment groups with an analysis of covariance using baseline levels as a covariate. If there is no pharmacokinetic interaction then we expect that there will be no statistically significant results for these analyses.

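### The between-arm celecoxib test only re-detects treatment assignment, and the escitalopram test takes no account of flexible dosing

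*Combined protocol and SAP*

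**What the plan says.** For Specific Aim 2 (DATA ANALYSIS AND STATISTICAL METHODS, I. Statistical Analysis), the plan is that "blood levels of escitalopram and celecoxib drawn at weeks 4 and 8 will be compared for patients in the two treatment groups", by analysis of covariance with the baseline level as the only named covariate. It then states: "If there is no pharmacokinetic interaction then we expect that there will be no statistically significant results for these analyses". The plural covers both drugs.

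Under STUDY TREATMENTS AND COMPLIANCE, every randomised patient receives open-label escitalopram plus "double-blinded treatment of celecoxib (fixed at 400mg/day) or placebo". The same section says: "Escitalopram doses may be optimized based on efficacy and tolerability over the 8 weeks of active treatment".

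The purpose runs in both directions. Measurement of Blood Levels of Celecoxib and Escitalopram wants to learn "if celecoxib changes escitalopram blood levels, or vice versa", alongside compliance and adequacy of dosing. Item 4 of III. Second Tier Exploratory Endpoints says the levels "will tell us if these two agents interfere or promote each other" in uptake or clearance. Of that whole tier the plan says: "Our study is not powered for them".

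**The concern.** Three things do not fit together.

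- **Celecoxib levels between arms.** One arm takes the drug and the other takes placebo. The levels differ by design, so the test says nothing about interaction. Its near-certain significance also contradicts what the plan expects when there is no interaction.
- **Escitalopram's effect on celecoxib.** This needs patients on celecoxib without escitalopram, and there are none.
- **Celecoxib's effect on escitalopram.** Both arms take escitalopram, so this is a proper randomised contrast. But dose can change after randomisation in response to efficacy and tolerability, which celecoxib may itself alter. A raw level mixes dose with clearance. If doses diverge, the comparison could show an interaction that is absent or hide one that is present.

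At stake is the answer to the pharmacokinetic part of Specific Aim 2, for which this is the only planned analysis.

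**Working it through.** **Inputs from the documents.** Two arms, 1:1, with no celecoxib-alone arm. Both drugs are given as placebo in the run-in, so baseline study-drug levels should be about zero. Planned sizes are 35 per arm at LUMC and 45 per arm overall. The plan gives no figure for the drug-level analysis. Its one calculated sample size, for HAM-D, reproduces: 2(1.96 + 0.8416)²/0.60² = 43.6, or 44.6 with the t distribution, hence 45 per group (two-sided 0.05, 80% power). It is used here only to set n.

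**Assumptions, not in the documents.** CVs; lognormal levels with σ² = ln(1 + CV²); levels proportional to dose; the dose splits below.

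**Step 1: baseline covariate.** A baseline of zero for everyone is a constant and adjusts nothing. The ANCOVA then reduces to a two-sample t-test.

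**Step 2: celecoxib.** With placebo-arm levels at 0, the pooled variance is s²/2, where s is the active-arm SD. The standard error is √(s²/2 × 2/n) = s/√n, so t = √n / (observed CV).

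- n = 35: √35 = 5.92 and the critical value is about 2.00, so non-significance needs an observed CV above about 3.0.
- n = 45: √45 = 6.71 and the critical value is about 1.99, so it needs an observed CV above about 3.4.

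Simulation with 20,000 trials per cell gave 100% significant for CV 0.3 to 0.7. At CV 1.5 it gave 99.5% (n = 35) and 99.8% (n = 45). With 20% of the celecoxib arm at zero and CV 1.5, the rates were 99.2% and 99.6%. With 50% at zero and CV 1.2 (1,000 trials), they were 98.8% and 99.3%.

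**Step 3: escitalopram, no true interaction, 45 per arm.** Entries are the percentage of trials significant.

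| Dose scenario | CV 30% | CV 50% | CV 70% |
|---|---|---|---|
| Equal doses, raw | 5 | 5 | 5 |
| 20% vs 50% at twice the starting dose, raw | 62 | 40 | 26 |
| Same split, log dose-normalised | 5 | 5 | 5 |
| Uniform ratio 1.10, raw | 33 | 14 | 10 |
| Uniform ratio 1.25, raw | 94 | 56 | 32 |

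The 20% vs 50% split has a mean dose ratio of 1.50/1.20 = 1.25. The uniform 1.25 row is an upper case, because it adds no dose variation within arms. A log-scale check of that row at CV 50%: σ = √ln 1.25 = 0.472; standard error = 0.472 × √(2/45) = 0.0996; ln 1.25 / 0.0996 = 2.24; power ≈ Φ(2.24 − 1.96) = 0.61, against 0.60 simulated on the log scale.

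Other splits (placebo arm vs celecoxib arm at twice the starting dose, log scale, CV 40% to 80%) gave 12% to 24% for 60% vs 40%, and 40% to 77% for 70% vs 30%. After dose-normalisation these stayed at about 5% to 6%.

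**Step 4: masking.** Take a true 25% rise in escitalopram with 66% (placebo arm) vs 34% (celecoxib arm) at twice the starting dose. The raw geometric mean ratio is 1.25 × 2^(0.34 − 0.66) = 1.00. Raw power is about 5%. Dose-normalised power is 78%, 46% and 32% at CV 40%, 60% and 80%.

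**Step 5: what a null result would exclude.** The 90% confidence factor is exp(t₀.₉₅,₂ₙ₋₂ × σ × √(2/n)). Around a ratio of 1.0, at CV 30%, 50% and 70%:

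- 45 per arm: 0.90–1.11, 0.85–1.18, 0.80–1.25.
- 35 per arm: 0.89–1.12, 0.83–1.21, 0.78–1.29.

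**The case against.** The celecoxib half has no answer: nothing in the documents qualifies the comparison or adds a celecoxib-alone group. The serious objections concern the rest.

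- **The dose problem is conditional.** One optimisation rule applies to both arms and celecoxib is blinded, so doses diverge systematically only if celecoxib changes efficacy or tolerability. No document predicts this. That stands, and the bias is a possibility only. The trial's own hypothesis is, however, that celecoxib improves mood response.
- **Raw levels have a meaning.** They estimate celecoxib's total effect on escitalopram exposure, including any effect through dose choice. True, but item 4 of the exploratory endpoints asks about uptake and clearance, which raw levels do not isolate.
- **The scenarios are chosen.** The dose splits are assumed, the masking case is set to cancel exactly, and the 5% after normalisation follows from assuming proportionality. All correct; the figures show sensitivity and are not forecasts.
- **The plan states an expectation, not a decision rule.** It does not say that non-significance proves no interaction. This is fair. The expectation is still false for celecoxib, and a null escitalopram result in an unpowered analysis needs an interval to be readable.
- **Dose may already be recorded.** I. Compliance says "The returned capsules will be counted" and mentions assays, but it is not a data-capture list. Silence there does not show that dose goes unrecorded.

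**Conclusion.** The concern holds. The celecoxib comparison is uninformative by design, which follows from the two arms and needs no assumed number; the 99% figures only confirm it. Escitalopram's effect on celecoxib is not estimable between arms, although two sections promise it.

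The escitalopram comparison is sound when doses match (5% false positives). If they diverge, its error depends on the assumed split and CV: 26% to 62% in the main scenario. Dose-normalisation removes that error if levels are proportional to dose.

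The consequence is limited. This is an unpowered exploratory endpoint. The HAM-D sample size, the adverse-event tables and the bleeding monitoring are untouched. It should be fixed because the error is certain for celecoxib and the correction is cheap.

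**What to change.** In the Specific Aim 2 analysis:

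1. Delete the between-arm celecoxib comparison and the sentence that ties an absence of significant results to an absence of interaction.
2. Compare log dose-normalised escitalopram trough levels (level divided by current daily dose) between arms at weeks 4 and 8. Report the geometric mean ratio with a 90% confidence interval, and the current escitalopram dose by arm.
3. State the assumptions: levels proportional to dose, and steady state at the draw. Report time since the last dose change.
4. State that escitalopram's effect on celecoxib cannot be estimated between arms, and that any association within the combination arm is descriptive. Align the exploratory endpoint and blood-level sections with this.
5. Keep celecoxib levels for the compliance and adequacy-of-dosing checks already planned.
6. Use pharmacokinetic throughout; the paragraph now also says pharmacodynamic. Dropping the baseline covariate is optional.

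The cost is plan wording, with assays already scheduled. Current escitalopram dose and the date of the last change must be available for each draw. One stated question is withdrawn as a between-arm test.

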## STUDY DESIGN

This is a 10-week, randomized, double-blind, two-arm, placebo-controlled study. The study includes a screening visit, a 1-week washout phase, a 1-week placebo run-in phase and an 8-week flexible dose phase. A minimum of 70 subjects will be randomized. The randomization code will be created and kept by the pharmacist in sealed envelopes for each individual subject. The PI will have access to the randomization code through the pharmacist if there is a medical safety issue.

At the screening visit, subjects will undergo a psychiatric interview. The diagnosis of Bipolar Depression (BPD) will be established in this examination using portions of the MINI. The study will be explained to all subjects. If a subject meets inclusion criteria, he or she will be asked to review the consent form and agree to participate. Subjects who meet the screening criteria and sign the IRB-approved consent form will undergo comprehensive assessments in order to quantify depression and associated symptoms.

At the end of the screening visit, subjects will be instructed how to taper the antidepressant they have been taking over the course of one week. A one-week taper is sufficient for all antidepressant medications except fluoxetine. Subjects taking fluoxetine will undergo a two-week taper/wash-out. After the taper, all subjects will return for a second visit to be placed on a 1-week single-blind placebo run-in. At the second screening visit, the subject will provide a saliva sample prior to undergoing assessments. Subjects will be instructed how to take pills (escitalopram placebo 10mg/day and celecoxib placebo 400mg/day) until the next visit one week later. Due to the fact that a one-week placebo run-in may be insufficient for some patients to reliably establish whether or not they are placebo responders, there will be an option to extend the placebo run-in for one additional week, at

the discretion of the PI. No increased risks are anticipated with the extension of the placebo phase, as patients are evaluated weekly and in close telephone contact.

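### The Aim 2 escitalopram comparison takes no account of dose, so if flexible dosing comes to differ by arm it can mimic or hide an interaction with celecoxib

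*Combined protocol and SAP*

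**What the plan says.** Specific Aim 2 asks, among other things, whether the two drugs interact pharmacokinetically. Item 4 of the Second Tier Exploratory Endpoints says that the blood levels "will tell us if these two agents interfere or promote each other's uptake and/or clearance". The same section calls these endpoints exploratory and says the study is not powered for them.

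The analysis is in Data Analysis and Statistical Methods, I. Statistical Analysis: "blood levels of escitalopram and celecoxib drawn at weeks 4 and 8 will be compared for patients in the two treatment groups". The method named is ANCOVA, and the pre-treatment level is its sole adjustment. The intended reading follows: "If there is no pharmacokinetic interaction then we expect that there will be no statistically significant results for these analyses".

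On dosing, Study Design describes "an 8-week flexible dose phase". Study Treatments and Compliance gives "open-label escitalopram (beginning at 10mg/day) + double-blinded treatment of celecoxib (fixed at 400mg/day) or placebo" and adds: "Escitalopram doses may be optimized based on efficacy and tolerability over the 8 weeks of active treatment". Before the baseline sample, patients taper their previous antidepressant and then "will receive one week of single-blinded escitalopram placebo + single-blinded celecoxib placebo".

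The Blood Sampling section standardises the draw to a trough about 12 hours after the last dose. No section divides the level by dose, adjusts for dose, restricts the comparison to one dose, or plans a comparison of dose between arms.

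**The concern.** A measured escitalopram level reflects both the dose taken and how the patient clears the drug. Only the second bears on an interaction. Once dose can move with efficacy and tolerability, dose at the week 4 and week 8 draws is a post-randomisation outcome, and it may differ between arms for two reasons.

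- **Efficacy.** The trial expects better mood scores with celecoxib. If doses are raised more often in patients who are doing less well, control patients could be on higher doses and show higher levels with no interaction at all.
- **Tolerability.** If celecoxib did raise escitalopram levels, dose adjustment for tolerability in that arm could offset the rise and hide it.

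The baseline level does not help. It is drawn after taper and placebo run-in, so it should be near zero for nearly everyone and says nothing about the later dose. Trough sampling controls timing only.

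At stake is the escitalopram half of the interaction question in Aim 2. The celecoxib half is a different matter, since celecoxib is at a fixed dose and is given in one arm only.

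**Working it through.** **Plan's own figure.** The documents give no sample size or power for the level comparison. The check borrows the primary-outcome size of 45 per group (effect size 0.60, 80% power, alpha 0.05). That figure reproduces: the normal approximation gives n = 2(1.960 + 0.842)²/0.60² = 43.6, rounded up to 44; the t-test version gives 44.6, rounded up to 45, with 80.4% power. The calculation is therefore two-sided, and two-sided 0.05 is used below.

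**Assumptions not in the documents.** Each patient is on 10 or 20 mg/day at the draw; level is proportional to dose; levels are log-normal with between-patient CV 40–60%, so the log-scale SD is √ln(1 + CV²), or 0.385 to 0.555. These values only illustrate the mechanism. The pre-treatment level is left out because it carries no information.

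**Size of the distortion.** If a share p of an arm is on the doubled dose, its mean level is proportional to 1 + p. The combination/control ratio of mean raw levels is then g × (1 + p_comb)/(1 + p_ctrl), where g is the true interaction ratio. The rejection rates come from simulation, with 10,000 or more trials per scenario and a two-sample t-test on raw levels or on log(level/dose). The lower end of each range belongs to the higher CV.

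| Higher dose, control/combination | g | Ratio of raw means | Raw test rejects | Log dose-normalised test rejects |
|---|---|---|---|---|
| equal | 1.00 | 1.00 | about 5% | about 5% |
| 55%/45% | 1.00 | 1.45/1.55 = 0.94 | 7–9% | about 5% |
| 60%/40% | 1.00 | 1.40/1.60 = 0.875 | 15–22% | about 5% |
| 70%/30% | 1.00 | 1.30/1.70 = 0.76 | 45–68% | about 5% |
| equal | 1.25 | 1.25 | 31–49% | 47–77% |
| 55%/45% | 1.25 | 1.25 × 0.935 = 1.17 | 16–27% | 47–78% |
| 60%/30% | 1.25 | 1.25 × 1.30/1.60 = 1.02 | about 5% | 47–78% |

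Hand check of the last column at g = 1.25: ln 1.25 = 0.223 and the standard error is SD × √(2/45), or 0.081 to 0.117. So z runs from 2.75 down to 1.91, and power from about 78% down to about 48%.

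A separate run with other assumptions agrees. With no interaction and CV 30, 50 and 70%, the raw test rejects in 10.8, 7.9 and 6.9% of trials when 50% of control and 40% of combination patients are on the doubled dose. At 50% and 30% it rejects in 30.7, 19.5 and 13.3%. With 35 per arm the latter become 25.4, 16.5 and 11.6%.

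**How much imbalance is plausible.** The sample-size section anticipates an effect of about 0.60 at week 2, built up from 0.52–0.53 in earlier studies. If dose were decided entirely by whether a patient fell above or below the overall median response, an effect of 0.53 to 0.60 would put Φ(0.265) = 60% to Φ(0.30) = 62% of control patients on the higher dose, against 38–40% of the combination arm. So 60/40 already requires dosing that follows response almost mechanically. A 70/30 split needs a separation of 2 × 0.524 = 1.05 SD. The plan expects the effect to grow after week 2 but gives no such figure.

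**Dose as a covariate.** Adding log dose to the model looks like a natural alternative. It was simulated with no interaction and dose doubled only when response was poor (90% of control, 50% of combination patients) and the patient's level at the starting dose was below a tolerability cut-off. That test rejected the true null in roughly 30–35% of trials; dose-normalised log levels stayed at about 5%. In this setting dose depends on the patient's own exposure, so conditioning on it biases the arm effect.

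**The case against.** The strongest reply is that little hangs on this test. The levels are second-tier, exploratory and unpowered, the project is described as proof-of-concept, and no dosing or stopping decision is tied to the result. The sentence about non-significance is worded as an expectation and is not a formal decision rule. The documents say only that doses may be optimised; they give no dose range, dose distribution or variability. With equal doses the raw comparison is unbiased, and with mild imbalance the inflation is small.

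All of that stands, and it limits the weight of the point. It does not remove it: lack of power excuses an imprecise estimate, not one that mixes dose with clearance, and drug interaction is named in a specific aim.

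Three stronger readings are tempting and are not supported:

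- A reader might infer that control patients will be titrated higher, so that a clinically successful trial yields a false interaction. The documents make this possible, not certain; the direction and size of any imbalance are unknown.
- A reader might take the 5% detection figure at 60/30 as typical. It is a near-exact cancellation (1.25 against a mean-dose ratio of 1.60/1.30 = 1.23). At 55/45 the raw test still detects the same interaction in 16–27% of trials.
- A reader might extend the point to the celecoxib levels. Celecoxib dose is fixed, so this mechanism does not apply.

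**Conclusion.** The point holds conditionally. If escitalopram dose differs by arm at the draws, the planned comparison can show a difference with no interaction or hide a real one. The stated reading, that no interaction means no significant result, therefore does not follow from this analysis. Under the assumed doses, proportionality and CV of 40–60%, the false-positive rate runs from close to nominal (7–9% at 55/45) through 15–22% at 60/40 to 45–68% at 70/30, the last being an extreme case. With equal doses the only loss is power: 31–49% against 47–77% for a true ratio of 1.25. None of these percentages is a prediction for this trial. The point concerns an exploratory endpoint and does not touch the primary HAM-D comparison, but it should be corrected before the levels are analysed.

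**What to change.** In the Aim 2 paragraph of the Statistical Analysis section:

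- Compare log dose-normalised escitalopram trough levels between arms at weeks 4 and 8, where the level is divided by the daily dose the patient was taking up to the draw (not a dose newly dispensed at that visit).
- Drop the pre-treatment level as covariate.
- Report the combination/placebo geometric mean ratio with its confidence interval, in place of the reading based on non-significance.
- Tabulate escitalopram dose by arm and visit.
- Do not use log dose as a covariate in the main analysis, because dose at the draw is a post-randomisation variable that can depend on the patient's own exposure.

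The cost is SAP wording, one derived variable and one table. Study drug is dispensed and returned capsules are counted from visit to visit, so dose should be derivable. The downside is an assumption that levels are proportional to dose, which should be stated. No sample, visit or dosing rule needs to change.

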At the Baseline visit, subjects will be reassessed for depression and associated symptoms. If subjects continue to score 18 or higher on the 17-item HAM-D scale, they will be randomized to receive escitalopram + celecoxib, or escitalopram + placebo in an assignment ratio 1:1. Subjects will then go on to complete assessments at Week 1, Week 2, Week 4 and Week 8. If the subject scores below 18 on the 17-item HAM-D scale at Baseline, he or she will be terminated from the study and classified as a placebo responder. At each of these visits, subjects will arrive 30 minutes before their scheduled appointment time, rest for 20 minutes in the exam room, and provide a saliva sample prior to undergoing any assessments. Terminated subjects will be offered conventional care at the same institution.

It is our desire to observe the diurnal nature of cortisol levels in saliva by measuring the patient's salivary cortisol levels at a time point prior to treatment and post treatment. At each of these two time points, we would collect saliva from the patient at five times during the day: upon awakening, approximately 30 minutes past awakening, before lunch, at approximately 3pm, and before bedtime. The patient would be required to do this at home and would then store the samples in their refrigerator until their next visit. Subjects will be provided with a log to record the exact time of saliva collection. We will be using salivettes purchased from Sarstedt Inc., and our Salivary Assay kits will be purchased from Salimetrics, LLC.

The overall study is powered for 90 subjects. We aim to randomize 70 subjects at LUMC. Approximately 30 subjects will be randomized by investigators at our sister site in Munich, Germany. At LUMC, 35 subjects will be randomized to each arm of the study. Subjects must complete 8 weeks of active medication to be considered study completers. We plan to enroll approximately 80 patients in anticipation of a 10% drop-out rate. The drop-out rate is based on our experience with our patient population over the past 5 years. If a subject drops out or is terminated after Week 6, their last observation will be carried forward in the analysis (LOCF). There are no healthy controls in this study because we already possess normative, untreated data for comparison.

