All statistical analyses will be conducted using the latest version of SPSS software for Windows. If a subject drops out after completing 6 weeks on active medication (after randomization), we will use the last observation carried forward (LOCF method) to analyze the data. If a subject has completed at least one week on active medication after randomization, but drops out of the study at any time between week-1 and week-8, s/he will be included in the intent-to-treat analysis. Since this project seeks to provide proof-of-concept in bipolar depression, and is therefore exploratory in nature, we propose the tests of significance use a 0.05 alpha level. However, if this proposal develops further we may adjust our desired level of statistical significance to be in line with the number of tests so that the family wise Type I error rate could be held at 5%. This issue will be considered in the future.

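### The plan defines a completer in two ways, and gives patients who leave between weeks 1 and 6 no week-8 value although it counts them in the intent-to-treat analysis

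*Combined protocol and SAP*

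**What the plan says.** **Completers.** Study Design states: "Subjects must complete 8 weeks of active medication to be considered study completers". The text below the Schedule of Events in Study Procedures sets the threshold at six weeks instead. Determination of Sample Size fixes the target at 90 patients who complete treatment and says that those lost will be replaced.

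**Missing values.** Study Design, Study Procedures and Statistical Analysis all confine carry-forward to patients who leave at about week 6 or later. In Statistical Analysis the wording is: "If a subject drops out after completing 6 weeks on active medication (after randomization), we will use the last observation carried forward". The sentence after it concerns patients with at least one week on medication; if such a patient "drops out of the study at any time between week-1 and week-8, s/he will be included in the intent-to-treat analysis". It assigns no value.

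**What needs a week-8 value.** The Primary Endpoint section lists three results: earlier response, greater HAM-D improvement at 8 weeks, and more remission at 8 weeks. Statistical Analysis plans an analysis of covariance at each post-baseline visit and a chi-square test on week-8 remission. The visits are fixed: "Subjects will then go on to complete assessments at Week 1, Week 2, Week 4 and Week 8".

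**Drop-out.** The only figure given is in Study Design: "We plan to enroll approximately 80 patients in anticipation of a 10% drop-out rate".

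**The concern.** Membership of an analysis set is not a rule for missing data. A patient who leaves at week 3 belongs to the intent-to-treat analysis but has no week-8 HAM-D score, falls outside the carry-forward rule, and has no stated remission status. The analyst must omit the patient, carry a score forward despite the six-week condition, or count the patient as a non-remitter. The plan names no mixed model, no imputation method and no missing-as-non-remission rule. A choice left open until the data are seen can favour one result, and remission is the result most sensitive to it.

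The two completer definitions matter because the sample size is expressed in completers and losses are replaced. A patient who leaves at week 7 counts toward the 90 under one definition and not under the other.

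**Working it through.** **1. The plan's own figure.** Determination of Sample Size gives an effect of 0.60 SD at week 2, alpha 0.05 and 80% power (two-sided assumed). The normal approximation is n = 2(1.960 + 0.842)² / 0.60² = 43.6, so 44 per arm. The t-based calculation gives 44.6, so 45. Power at 45 per arm is 80.4%. The stated 45 per group reproduces and is not in dispute.

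**2. The rules side by side.**

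| Leaves | In intent-to-treat set | Week-8 value |
|---|---|---|
| Before week 1 | No | None |
| Weeks 1 to 6 | Yes | No rule |
| After week 6 | Yes | Carried forward |

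**3. How many patients.** Assume the 10% drop-out is spread at a constant rate over 8 weeks, so the proportion remaining at week t is 0.9^(t/8).
- Before week 1: 1 − 0.9^(1/8) = 1.3 per 100.
- Weeks 1 to 6: 0.9^(1/8) − 0.9^(6/8) = 98.7% − 92.4% = 6.3 per 100.
- After week 6: 92.4% − 90.0% = 2.4 per 100.

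The stated rule covers 2.4 of 10 drop-outs, about a quarter. Completers number about 92 per 100 under the six-week definition and 90 under the eight-week one. The upper bound for early leavers at this drop-out rate is 10 per 100. For week 2, leavers between weeks 1 and 2 number 0.9^(1/8) − 0.9^(2/8) = 98.7% − 97.4% = 1.3 per 100.

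**4. Remission, assumed counts.** Take 50 per arm and 21 v 14 remitters, with no early leaver a remitter. The test is Pearson chi-square without correction.
- Missing counted as non-remission: 21/50 v 14/50, chi-square 2.15, p = 0.14.
- Omission, 6 early leavers: split 5 v 1, 21/45 v 14/49, p = 0.070; split 3 v 3, 21/47 v 14/47, p = 0.135; split 1 v 5, 21/49 v 14/45, p = 0.24.
- Omission, 10 early leavers: split 8 v 2, 21/42 v 14/48, p = 0.043; split 5 v 5, 21/45 v 14/45, p = 0.13; split 2 v 8, 21/48 v 14/42, p = 0.31.

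With equal drop-out in the two arms, a split of 5 v 1 or worse in either direction among 6 has probability 0.20, and 8 v 2 or worse among 10 has probability 0.09 (hypergeometric).

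**5. Choosing the rule after seeing the data.** The simulation used 200,000 trials per scenario, 50 per arm, assumed placebo remission of 20–40% among those who stay, and last-visit remission among early leavers at 25% or 50% of that rate.
- With no true difference, each single rule gives 4.9–5.4% false positives. The best of the three gives 6.0–6.6% with 6% early leavers per arm and 6.5–7.1% with 10%.
- With a true difference of 15–20 points, omission and non-remission fall on opposite sides of 0.05 in about 4–8% of trials (6% per arm) or 6–10% (10% per arm). Their power differs by at most 1.6 and 2.9 points.

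**6. Week-8 mean.** The standard error at 45 per arm is √(2/45) = 0.21 SD. The simulation assumed effects of 0.2, 0.4, 0.5 and 0.6 SD at weeks 1, 2, 4 and 8, with early leavers stopping after week 2. Omission bias is within 0.001 SD when non-response drives drop-out equally in both arms. When it does so in one arm only, the bias is 0.02–0.04 SD at 6% early leavers per arm and 0.03–0.06 SD at 10%. The sample-size section places 0.60 at week 2 and expects it to rise; using 0.4, 0.6, 0.7 and 0.8 SD instead barely changed the bias.

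**The case against.** The strongest reply is that little turns on this. The plan calls itself proof-of-concept and exploratory, leaves alpha unadjusted, and tests five scales at four visits; a further one or two points of false-positive risk is small beside that. Only one of the six omission splits above crosses 0.05, and it needs every drop-out to fall in weeks 1 to 6. With other assumed counts (23 v 13 remitters among 45 observed per arm, five early leavers in each) all three rules stay below 0.05: p = 0.031 for omission, 0.037 for non-remission, and 0.013 if two combination-arm leavers are carried forward as remitters. The covariance analysis is done visit by visit, so early leavers still contribute at visits they attended. A one-line rule would close the gap, and a mixed model is not immune: if drop-out depends on the unseen week-8 score in one arm only, it is off by 0.04–0.07 SD at 6% early leavers per arm, against 0.05–0.08 SD for omission.

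Most of this stands, and it limits the severity. It does not remove the gap. Exploratory status can excuse a lenient alpha, but not two definitions of one term or a primary analysis that cannot be run as written. It might also be said that the remission table, by sorting patients into remitters and others, already counts a missing score as non-remission. The text can be read that way but does not say so.

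**Conclusion.** The point holds and should be fixed, at modest severity. The completer definitions contradict each other, and two of the three primary results lack a value for early leavers. The sizes rest on the stated 10% drop-out together with assumed timing, arm split and remission rates: about 6 early leavers per 100, a remission false-positive rate of about 6–7% instead of 5%, and a week-8 bias of 0.02–0.06 SD only under one-sided informative drop-out.

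A reader might infer more, which the documents do not support:
- *That the powered comparison is compromised.* It is set at week 2, before most drop-out.
- *That the plan is really a completers-only analysis.* Omission is the likely software default for the covariance analysis, but no section prescribes it.
- *That excluding patients with under one week of medication is a serious bias.* They number about 1 per 100 and generally have no post-baseline score, because the first visit is at week 1.
- *That carry-forward after week 6 distorts the result.* There is no week-6 visit, so a week-4 score may be carried for some patients. With 2.4% late leavers per arm and an assumed 0.4 SD decline from week 4 to week 8, the shift is at most 0.003 SD; it reaches 0.02–0.03 SD only if 5% leave late in one arm alone.

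Which McGill score serves as covariate, and how the enrolment totals reconcile, are separate questions.

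**What to change.** 1. Use one completer definition in Study Design, Study Procedures and Determination of Sample Size.
2. Analyse HAM-D by randomised arm with one mixed model for repeated measures over weeks 1, 2, 4 and 8, using every patient with a post-baseline score and the covariates already planned. Read the week-2 and week-8 contrasts from it. Keep carry-forward as a sensitivity analysis, and report by arm the number with baseline data only.
3. Analyse week-8 remission in all randomised patients with missing status counted as non-remission, and add a multiple-imputation sensitivity analysis.
4. State that drop-outs who are replaced stay in the analysis as randomised.

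The cost is wording and slightly more analysis work, with no extra visits or patients. Stated remission rates will be lower in both arms, and the remission difference can shift if drop-out is unequal. The mixed model assumes data are missing at random. It also leaves out patients with no post-baseline score, so only the remission analysis covers everyone randomised.
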